6.3 Follow-up for Patients Withdrawn from Study Treatment

Patients withdrawn from study treatment with an ongoing adverse event must be followed clinically until the event is resolved, deemed stable or permanent by the PI, or the patient starts another treatment for their disease. A stable adverse event is defined as an event that is not expected to change in nature, severity or frequency. See [Section 8.4](#) through [Section 8.8](#) for reporting of adverse events. The pregnancy of any patient, or patient's partner, will be followed via monthly telephone calls until the birth of the child to term to record any birth defects/abnormalities.

7. CRITERIA FOR EVALUATION AND ENDPOINT DEFINITIONS

7.1 Safety Endpoints

Safety and tolerability of the regimen will be assessed by analyzing the incidence rates of treatment-emergent adverse events summarized at the MedDRA preferred term and primary system organ class levels. Similar summaries will be made for subsets of AEs such as (1) those judged by the Investigator to be related to study treatment, and (2) serious adverse events (SAEs).

Other routine safety assessments (eg, clinical laboratory parameters and vital signs) will be summarized by shift tables and treatment group using mean, standard deviation, median, minimum and maximum changes from baseline values.

Mortality (all causes) at 30 and 60 days following last treatment will also be calculated. Adverse events will be graded according to National Cancer Institute's Common Terminology Criteria for Adverse Events (NCI CTCAE), version 5.0.

A Data Safety Monitoring Board (DSMB) will monitor key outcomes from the study.

7.2 Efficacy Endpoints

Primary Endpoint

- Combined Complete Remission Rate = CR + CRi as defined by the International Working Group Criteria and 2017 European LeukemiaNet

Secondary Endpoints

- Median Overall Survival (OS) = Time from treatment (Day 1) until death from any cause
- CR_{MRD-} = Percentage of patients achieving complete response (CR) whose bone marrow is determined to be negative for MRD using standardized techniques (ie, MPFC and molecular testing including NGS)
- CR Rate = Percentage of patients achieving:
 - CR = Bone marrow blasts <5%; absence of blasts with Auer rods; absence of extramedullary disease; hematologic recovery (absolute neutrophil count [ANC] ≥1000/µL and platelet count ≥100,000/µL)

- Composite CR rate = Combined percentage of patients achieving one of the following:
 - CR
 - CRi = Meets all CR criteria but with only full recovery of one peripheral blood cell type (ie, ANC \geq 1000/ μ L **or** platelet count \geq 100,000/ μ L)
 - CRh = Meets all CR criteria but with only partial recovery of **both** peripheral blood cell types (ie, ANC \geq 500/ μ L **and** platelet count \geq 50,000/ μ L)
- Combined Response rate = Combined percentage of patients achieving one of the following:
 - CR
 - CRi
 - CRh
 - Morphologic leukemia-free state (MLFS) = Bone marrow blasts <5%; absence of blasts with Auer rods; absence of extramedullary disease; no hematologic recovery required
 - Partial Response (PR) = Meets all hematologic values required for CR but with a decrease of at least 50% in the percentage of blasts to \geq 5% to \leq 25% in bone marrow
- Event-free Survival (EFS) = Time from first treatment (Day 1) until (a) treatment failure, (b) relapse after CR/CRi/CRh, or (c) death from any cause, whichever occurs first, censored at 2 years
- Duration of Composite CR = Time from first documented response of CR, CRi, or CRh to relapse or death from any cause
- Rates of 28- and 56-day Transfusion Independence (TI) = Percentages of patients who do not receive red blood cell (RBC) transfusions, platelet (PLT) transfusions, and neither RBC nor PLT transfusions for 28 and 56 days; comprised of 6 secondary endpoints:
 - 28-day RBC TI
 - 28-day PLT TI
 - 28-day TI (both RBC and PLT)
 - 56-day RBC TI
 - 56-day PLT TI
 - 56-day TI (both RBC and PLT)

28- and 56-day TI will be summarized in 2x2 shift tables showing the percentages of patients who are transfusion independent at baseline according to review of medical charts versus the percentages of patients who achieve transfusion independence at any time during the study.

Effort will be made to collect transfusion information for 56 days following withdrawal from the study to properly classify a patient's post-treatment TI status. Patients not already classified as transfusion independent and who cannot be followed will be classified as 'status unknown' for the required time to establish TI.

Exploratory Endpoints

- To evaluate potential biomarkers including but not limited to MCL-1 dependence, genetic mutations, and other biomarkers associated with AML.
- Additional exploratory analyses may be performed if useful in the interpretation of the data.

7.3 Pharmacodynamic Endpoints

Pharmacodynamic endpoints include:

- BH3 profiling, including determination of MCL-1 dependence, at Baseline and End of Treatment using bone marrow.
- Minimal residual disease (MRD) to be determined by central CLIA accredited laboratory evaluation of bone marrow samples collected at baseline and at time of response assessments using standardized techniques (ie, MPFC and molecular testing including NGS).
- Peripheral blood and bone marrow samples will be collected at protocol-specific time points to evaluate other potential biomarkers including but not limited to MCL-1 dependence. These assessments may be explored in the context of AML or related conditions or drugs of similar class.

8. ADVERSE EVENTS

8.1 Definitions

An adverse event (AE) is defined as any untoward medical occurrence associated with the use of a drug in humans, whether or not considered drug related. An AE can therefore be any unfavorable and unintended sign (including an abnormal laboratory finding), symptom, or disease temporally associated with the use of a drug, whether or not related to the drug product.)

Suspected adverse reaction means any adverse event for which there is a reasonable possibility that the drug caused the adverse event. For the purposes of IND safety reporting, 'reasonable possibility' means there is evidence to suggest a causal relationship between the drug and the adverse event.

Unexpected adverse event or unexpected suspected adverse reaction: An adverse event or suspected adverse reaction is considered unexpected if it is not listed in the current [Investigator's Brochure](#) or is not listed at the specificity or severity that has been observed; or, is not consistent with the risk information described in the general investigational plan (clinical study protocol).

Toxicities will be assessed according to the NCI CTCAE, version 5.0 (see [Appendix C](#)). When the NCI CTCAE grade is not available, the Investigator will use the following toxicity grading: mild, moderate, severe, life-threatening or fatal.

GRADE 1 – Mild:	Transient or mild discomfort; no limitation in activity; no medical intervention/therapy required.
GRADE 2 – Moderate:	Mild to moderate limitation in activity – some assistance may be needed; no or minimal medical intervention/therapy required.
GRADE 3 – Severe:	Marked limitation in activity, some assistance usually required; medical intervention/therapy required, hospitalizations possible.
GRADE 4 – Life Threatening:	Extreme limitation in activity, significant assistance required; life threatening (immediate risk of death); significant medical intervention/therapy required, hospitalization or hospice care probable.
GRADE 5 – Fatal:	Results in death.

8.2 Causality

Relationship of the adverse event (AE) to the study drug should be defined as follows:

Unrelated:	AE is clearly not related to the investigational agent(s)
Unlikely:	AE is doubtfully related to the investigational agent(s)
Possible:	AE may be related to the investigational agent(s)
Probable:	AE is likely related to the investigational agent(s)
Definite:	AE is clearly related to the investigational agent(s)

8.3 Serious Adverse Events

A serious adverse event (SAE) is defined as any experience that suggests a significant hazard, contraindication, side effect, or precaution. An SAE includes:

- Any death, or
- Any life-threatening event (ie, the patient is at immediate risk of death from the event as it occurred), or
- Any event that is persistently, significantly, severely or permanently disabling, or requires intervention to prevent such disability, or
- Any event which requires inpatient hospitalization or prolongs hospitalization, or
- Any congenital abnormality/birth defect, or
- Any medically significant event that may jeopardize the patient or may require intervention to prevent one of the other outcomes listed above.

In addition, any adverse event which results in termination of the patient from study will be considered a potentially serious adverse event and must be reported to the Sponsor as described in [Section 8.4](#).

Bone marrow suppression and associated complications are expected events during leukemia therapy and are part of the treatment process (marrow emptying of leukemic cells). Therefore, hospitalization or prolongation of hospitalization for myelosuppression and associated complications directly

related to the myelosuppression, such as fever, infections and bleeding, will not be reported as serious adverse events (SAEs), but will be reported as adverse events on the adverse event case report form and will be summarized in the updated and final reports. Anemia and thrombocytopenia will not be reported as an SAE. Prolonged bone marrow suppression (as defined by the NCI toxicity criteria specific for leukemia, ie, bone marrow cellularity <5% on Day 42 or later (6 weeks) from start of therapy without evidence of leukemia) or the unexpected nature, severity or frequency of myelosuppression, anemia, and thrombocytopenia or an associated complication will be reported as an SAE.

8.4 Eliciting and Reporting Adverse Events

All adverse events, regardless of severity, which occur during the study, will be documented in the study progress notes, and the “Adverse Event” case report form will be completed. This includes both serious and non-serious events. Adverse events occurring from the time of the first dose will be captured.

All adverse events noted by study staff or volunteered by study patients at any time will be recorded. The Principal Investigator or a qualified designated staff physician will conduct clinical assessments of all patients at each scheduled clinic visit. In addition, patients will be queried about any adverse symptoms they have experienced since the previous study visit. In order to avoid bias in eliciting events, suggestive questioning of the patients shall not occur.

A laboratory abnormality must be reported on the “Adverse Event” case report form only if it is the main causative factor of an SAE, requires a therapeutic intervention, or is the reason the patient is coming off treatment. For laboratory abnormalities that require reporting on an Adverse Event case report form, clinical sites should enter only the highest CTCAE severity grade of the test result and document the start and end dates at the highest grade. However, all laboratory assessments, whether required according to the protocol’s schedule of events or an unscheduled assessment performed according the site’s Good Medical Practices, should be entered into the clinical database on the appropriate laboratory test results case report form (e.g., Hematology or Serum Chemistry). Additional details are provided in the electronic case report form (eCRF) Completion Guidelines.

Adverse events will be reported and described in terms of intensity, seriousness and causality, based on the Principal Investigator’s judgment using protocol-defined definitions. Necessary counter measures will also be reported on the appropriate case report form used to collect concomitant medications.

8.5 Serious Adverse Events and/or Adverse Events Requiring Discontinuation of Study Drug

Any serious adverse event (SAE) or unexpected AE \geq NCI CTCAE Grade 3 that occurs during this study and up to 30 days after discontinuation of study drug must be reported to the Study Medical Monitor within 24 hours of the Principal Investigator's awareness of the event, whether or not this reaction is considered to be associated with use of the investigational drug.

In addition, the occurrence of any AE leading to permanent discontinuation of study drug must also be reported to the Sponsor within 24 hours of the Principal Investigator's awareness of the event.

Serious adverse events must be scanned and emailed to the Sponsor/Study Medical Monitor.

Email to: [REDACTED]

It is expected that the Principal Investigator will provide or arrange appropriate supportive care for the study patient. A patient experiencing a serious adverse event(s) should be followed clinically until the event is resolved, deemed stable or permanent, or the patient starts another treatment for their disease. All telephone and scanned/mailed reports must be followed with a written Serious Adverse Event (SAE) report form within 24 hours of the Principal Investigator's awareness of serious adverse events and nonserious events which required discontinuation of study drug.

The (SAE) report form should be completed and signed by the Principal Investigator, scanned, and sent by email to the Sponsor as described above. The SAE Report Form is distinct and separate from the adverse event form included in the case report form.

Grades for all SAEs and AEs, regardless of whether they trigger expedited reporting or not, must still be captured by the CRF.

8.6 Follow-up of Adverse Events

Adverse events, which are identified on the last scheduled visit, must be recorded on the AE CRF page and reported to the Sponsor according to the procedures outlined in Section 8.4.

Patients with unresolved previously reported adverse events or new adverse events identified on the last scheduled visit should be followed by the Principal Investigator until the events resolve, are deemed stable or permanent, or the patient starts another treatment for their disease. Resolution means the patient has returned to his/her baseline state of health or the Principal Investigator does not expect any further improvement or worsening of the adverse event. The Principal Investigator should continue to report any significant follow-up

information to the Sponsor up to the point the event has resolved. Any adverse events reported by the patient to the Principal Investigator which occur after the last scheduled visit, and are determined by the Principal Investigator to be reasonably associated with the use of the study drug or meet the criteria of a reportable adverse event as described above, should be reported to the Sponsor.

Patients withdrawn from the study with an ongoing adverse event must be followed clinically until the event is resolved, deemed stable or permanent, or the patient starts another treatment for their disease. A stable adverse event is defined as an event, which is not expected to change in nature, severity, or frequency. The Principal Investigator should continue to report any significant follow-up information to the Sponsor.

8.7 Patient Deaths

Every effort will be made in the case of patients who die to determine the cause of death. Information regarding a patient who dies more than 30 days after receiving study drug may be recorded on a Death Report Form (no SAE report is required). An SAE report is recorded only if the event leading up to the patient's death began within 30 days of the last administration of study drug.

The Death Report Form is distinct and separate from the adverse event form included in the case report form.

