In the Phase 1 dose-escalating study [37], dose-limiting toxicity of alvocidib in bolus ACM occurred at 60 mg/m²/d with profound neutropenia >40 days duration, with the maximal tolerated dose (MTD) of 50 mg/m²/d. Mild TLS was observed in 9/34 (26%) of patients, with no relapsed or refractory AML patients requiring dialysis. Induction-related mortality was observed in 4/34 (12%) of patients; 2 with fungal sepsis and 2 cardiac-related deaths. Adverse events Grade ≥ 3 included: 6% diarrhea, 9% oral mucositis and 9% gastrointestinal mucositis and 6% neutropenic fever/infection (with 1 Grade 5 fungal infection).

2.6.2.2 Summary of Safety in NCI-3170 (J-0254) FLAM Extension in Adults with Refractory or Relapsed Poor-risk Acute Leukemias (Phase 2)

In the J0254 Phase 2 “Extension Study” [38], all-grade TLS was observed in 15/47 (32%) of the relapsed/refractory AML patients, with one patient requiring dialysis, and all-grade TLS was noted in 9/15 (60%) patients with newly diagnosed secondary AML. Treatment-related induction mortality was observed in 3/62 (5%) of patients, due to fungal infection and multi-organ failure. Other AEs Grade ≥ 3 included 5% arrhythmia and decreased left ventricular ejection fraction, 2% GI mucositis, and 5% fungal infection/multi-organ failure.

2.6.2.3 Summary of Safety in NCI-6947 (OSU-0479) Alvocidib Monotherapy in Relapsed/Refractory AML (Phase 1)

Alvocidib was given as a *hybrid* regimen: 30-minute IV bolus followed by a 4-hour continuous IV infusion, daily for 3 days. A second cycle of treatment was permitted, based on a 21-day cycle, depending on cytoreduction. Dosing began at 20 mg/m² IV bolus and 30 mg/m² continuous IV infusion (ie, ‘20/30’) with escalation by approximately 25% increments following a classic 3+3 phase I design schema to determine the MTD of the schedule. Clinical TLS occurred in a single AML patient (1/19, 5%) who required dialysis [39]. This patient was the only treatment-related death, due to a subsequent fungal infection. Among all 19 AML patients and 5 ALL patients treated with monotherapy alvocidib, AEs Grade > 3 included: 58% neutropenic fever/infection, 42% fatigue, 29% diarrhea, 13% decreased ejection fraction, 4% hypotension at the 40/60 mg/m² dose level, 4% prolonged QT at the 30/35 mg/m² dose level, and 4% mucositis.

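### Section 8.7 allows no SAE report for a drug-related death whose causal event starts more than 30 days after the last dose, and it does not fit the reporting rules in 8.5 and 8.6

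*Protocol*

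**What the plan says.** Four sections of the Protocol bear on the same death.

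- **8.3** counts any death as a serious adverse event.
- **8.5** says that any SAE "that occurs during this study and up to 30 days after discontinuation of study drug must be reported". The deadline is 24 hours from the investigator's awareness, the attribution does not matter, and a written SAE form must follow.
- **8.6** deals with events that the patient reports after the last scheduled visit. They should go to the Sponsor if they "are determined by the Principal Investigator to be reasonably associated with the use of the study drug", or if they meet the reporting criteria given earlier. It sets no end date and names no form.
- **8.7** makes a Death Report Form optional when the patient dies more than 30 days after study drug. Its text then runs: "no SAE report is required). An SAE report is recorded only if the event leading up to". The sentence goes on to set the limit at an onset no later than 30 days after the final dose.

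No passage says which rule prevails. Section 5.4 treats the last dose and the decision to discontinue as two separate dates. The treatment-emergent window in Protocol 11.4.3 runs 30 days from the last administration, the same start point as 8.7.

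**The concern.** A site that follows 8.7 literally would file no SAE form for a fatal event that starts more than 30 days after the last dose, even if the investigator judges it drug-related. The 24-hour notice in 8.5 is tied to SAEs. Under 8.8 the Sponsor's expedited reporting and the investigator's notice to the ethics board depend on those reports reaching them. For late deaths 8.7 makes even the Death Report Form optional.

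Late toxicity is not remote in this Protocol. Section 8.3 itself makes prolonged marrow suppression an SAE when it is present "on Day 42 or later (6 weeks) from start of therapy without evidence of leukemia", so the plan expects toxicity to matter at about the time the 30-day window after a Day 15 dose runs out.

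**Working it through.** The plan states no figure to reproduce. The check is a comparison of texts plus a day count.

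**Step 1. The two tests inside 8.7.** Suppose sepsis starts 20 days after the last dose and the patient dies on day 35 after it. The first sentence looks at the date of death (35 > 30) and requires no SAE report. The second looks at onset (20 ≤ 30) and treats the event as one for an SAE report. The section does not say which test decides. The waiver in the first sentence is only permissive; the bar comes from the words *only if* in the second.

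**Step 2. 8.5 against 8.7.** Let L be the day of the last dose and D the day on which discontinuation is dated. The 8.7 window closes on L + 30 and the 8.5 window on D + 30, so the mismatch is D − L.

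Inputs:
- L = Day 15, the last scheduled dose of a cycle in both arms (Protocol 4.4.2).
- D is not defined. Three candidate dates are the last dose itself; the Day 28 marrow assessment (5.2.6); and the 6-week limit between cycle starts (5.3), which is Day 1 + 42 = Day 43. These are assumptions, and visit windows are ignored.

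| Discontinuation dated at | 8.7 closes | 8.5 closes | Mismatch |
|---|---|---|---|
| Last dose, Day 15 | 15 + 30 = Day 45 | 15 + 30 = Day 45 | 0 days |
| Day 28 decision | Day 45 | 28 + 30 = Day 58 | 58 − 45 = 13 days |
| 6-week limit, Day 43 | Day 45 | 43 + 30 = Day 73 | 73 − 45 = 28 days |

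A fatal event that starts inside the mismatch must be reported under 8.5 and gets no SAE report under 8.7. This applies to related and unrelated events alike. If the words *during this study* in 8.5 include the 2-year telephone follow-up (5.5), the overlap is wider still; the Protocol does not settle that.

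**Step 3. 8.6 against 8.7.** Once the 8.5 window has closed, however it is dated, a related fatal event should still reach the Sponsor under 8.6. Because 8.6 states neither a form nor a deadline, and 8.7 excludes the SAE form, nothing clearly carries the event into the 24-hour procedure. This gap remains even when the mismatch in step 2 is 0.

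**The case against.** The case for leaving the text alone has several parts.

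*Discontinuation may simply mean the last dose.* Section 5.4 names the decision explicitly where it means the decision, and the treatment-emergent window runs from the last administration. On that reading the 8.5 and 8.7 windows coincide. This stands as a possible reading, so the 13 days cannot be given as the result; it is one point in a range that starts at 0.

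*8.6 and 8.7 can coexist.* A reader might infer that a late related death is flatly both reportable and not reportable. The text does not go that far. Section 8.6 speaks of events reported by the patient, says *should*, and names no form, so a notice to the Sponsor without an SAE form satisfies both sections. The clash is partial. What remains is the missing form and the missing deadline.

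*The two sentences of 8.7 may be a default and its qualifier.* That is a fair reading and would make step 1 loose drafting. It does not supply the missing exception for related events.

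*The link to late marrow toxicity is easily overstated.* A reader might set Day 42 in 8.3 against Day 45 and infer that only those few days are left for a fatal infection to count. The documents do not support this: suppression confirmed on Day 42 began earlier, can itself be the event that led to death, and is reportable in its own right under 8.3. A reader might also lean on the earlier dose-limiting "profound neutropenia >40 days duration" (2.6.2.1). That arose at 60 mg/m²/d in a regimen with cytarabine and mitoxantrone that neither arm here uses, so it does not show that fatal events will cluster after day 30.

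*Late deaths are recorded elsewhere.* Section 7.1 calculates all-cause mortality at 30 and 60 days after last treatment, section 5.5 collects dates of death for 2 years, and 8.7 asks for every effort to establish the cause. So deaths are not lost. None of these routes provides an SAE form or 24-hour notice.

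**Conclusion.** The concern holds as a gap and a mismatch in the safety-reporting rules. The firm part needs no assumption about dates: 8.7 excludes an SAE report for any fatal event that starts more than 30 days after the last administration, has no exception for drug-related events, and 8.6 does not clearly restore the 24-hour route. The mismatch between 8.5 and 8.7 is conditional, from 0 to 28 days over the three datings considered for a last dose on Day 15. The two tests inside 8.7 add avoidable ambiguity.

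Sample size, power and type I error are not affected. The practical reach is limited because the SAP (section 1) reports that the study closed with 11 patients enrolled. The text should still be corrected, since a site applying it literally would give a worse safety result and the correction is cheap.

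**What to change.** 1. Choose one start point for the 30 days, define it, and use it in both 8.5 and 8.7.
2. In 8.7, make onset of the causal event the only test. Delete the parenthesis that waives the SAE report on the basis of the date of death.
3. Add to 8.7 that an SAE report is also required, at any later time, if the fatal event is judged at least possibly related to study drug on the scale in 8.2.
4. In 8.6, cross-refer to the 8.5 procedure for such events, including its 24-hour limit and form, and remove the restriction to events reported by the patient.

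The cost is a wording change in three sections and a few additional SAE forms. Making the Death Report Form mandatory for all other deaths would be tidy but is optional; the correction does not depend on it.
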